6.5.8 HHD0 and HHD0²

Analyses of HHD0 are the same as specified in the M-SAP with the modification that treatment group is a three-level variable (i.e., placebo, 30 mg/d CNM-Au8, and 60 mg/d CNM-Au8), with addition of parallel analyses of HHD0², with a separate analysis that includes baseline serum NfL level as an additional covariate, and with the clarification that time to zero strength for both analyses is interval censored between HHD assessments.

Inference from these analyses is supportive of inference from the repeated-measures linear mixed model for HHD upper and lower extremity scores.

6.5.9 Quantitative Voice Measures

Given the high frequency of voice recordings, a repeated-measures analysis with unstructured covariance is overly flexible but the assumption of linear change required by the random-slopes model may be overly rigid. To complement estimates from the random-slopes linear mixed model, quantitative voice characteristics will be analyzed in a linear mixed model in which the temporal profile for both fixed and random terms is modeled using cubic B-splines with knots at 8 and 16 weeks. The model will include fixed terms for B-splines (4 terms), treatment group (3 levels), treatment group × B-spline interaction, centered time since symptom onset and centered time since symptom onset × B-spline interaction, centered delta-FRS and centered delta-FRS × B-spline interaction, centered baseline riluzole use and centered baseline riluzole × B-spline interaction, and centered baseline edaravone use and centered baseline edaravone × B-spline interaction. The model will include random regimen-specific intercepts and slopes with unstructured covariance, random participant-specific B-splines (5 terms) with unstructured covariance, and a first-order autoregressive structure for residuals. A simplified covariance structure assuming no regimen-level covariance, heterogeneous compound symmetric covariance among the random B-splines, conditional independence of residuals, or a combination of the three simplifying assumptions will be used if the full model fails to converge. The primary estimand will be the active (i.e., the average of both 30 mg/d and 60 mg/d dosage groups) vs. placebo treatment-dependent difference in 24-week change from baseline. The estimate and its 95% Wald confidence bounds will be obtained by a linear contrast of adjusted means.

A separate supportive analysis will include centered baseline serum NfL level and the interaction of centered baseline serum NfL level and B-splines as additional covariates.

6.5.10 Placebo Multiple Imputation

Placebo multiple imputation analyses are the same as specified in the M-SAP with the modification that treatment group is a three-level variable (i.e., placebo, 30 mg/d CNM-Au8, and 60 mg/d CNM-Au8). Placebo multiple imputation analyses will be applied to ALSFRS-R total score, HHD upper and lower extremity percentages, and SVC.

The following SAS code specifies the imputation for an endpoint measured every 8 weeks:

```
proc mi data=work.outcomes seed=xxx nimpute=50 out=work.out_mi01
    minimum=. . . . x x x x maximum=. . . . y y y y minmaxiter=1000;
    class rlz edv trtrnd;
    fcs reg(Wk08 = sx2b1 dFRS rlz edv Wk00);
    fcs reg(Wk16 = sx2b1 dFRS rlz edv Wk00 Wk08);
    fcs reg(Wk24 = sx2b1 dFRS rlz edv Wk00 Wk08 Wk16);
    mnar model( Wk08 Wk16 Wk24 / modelobs=(trtrnd="0"));
    var sx2b1 dFRS rlz edv Wk00 Wk08 Wk16 Wk24;
run;
```

where Wk00, Wk08, Wk16, and Wk24 are the values of a given efficacy endpoint at the Baseline, Week 8, Week 16, and Week 24 Visits, respectively, trtrnd has a value of zero (0) for participants randomized to placebo, and x and y take appropriate values to specify the range of a given outcome measure (i.e., 0 and 48 for ALSFRS-R total score; 0 and . for HHD upper and lower extremity percentages and SVC).

Inference from these analyses is supportive of inference from the Bayesian shared-parameter, repeated-measures model for the primary endpoint and assess sensitivity to the missing data assumption of the repeated-measures linear mixed model for secondary endpoints in the FAS analysis set. A separate analysis will include centered baseline serum NfL level as an additional covariate in both imputation stages.

6.5.11 Additional Sensitivity Analyses of Primary and Key Secondary Outcomes

Sensitivity analyses of primary and key secondary efficacy outcomes are the same as specified in the M-SAP with the modification that treatment group is a three-level variable (i.e., placebo, 30 mg/d CNM-Au8, and 60 mg/d CNM-Au8).

6.5.12 Subgroup Analyses

In addition to the subgroups specified in the M-SAP, the following additional subgroups will be analyzed in the random-slope model (see Section 6.5.5) for primary and secondary efficacy endpoints in the FAS analysis set:

- Baseline use of riluzole and edaravone (neither, riluzole only, edaravone only, both),
- Age (less than 65 years vs. 65 years or older),
- Sex (female vs. male),
- Race (white vs. any minority race with greater than 5% prevalence in the sample),
- Ethnicity (Hispanic or Latino vs. non-Hispanic or Latino),

- Weight (less than 43 kg, 43 to less than 56 kg, 56 to less than 77 kg, 77 to less than 150 kg, 150 kg or more),
- BMI (less than 18.5 kg/m², 18.5 to less than 25 kg/m², 25 to less than 30 kg/m², 30 to less than 40 kg/m², 40 kg/m² or more),
- Chronic kidney disease (CKD) stage (stage 1 or better [eGFR 90 mL/min/1.73m² or more], stage 2 [eGFR 60 to 89 mL/min/1.73m²], stage 3 [eGFR 30 to 59 mL/min/1.73m²], stage 4 [eGFR 15 to 29 mL/min/1.73m²], stage 5 [eGFR less than 15 mL/min/1.73m²]),
- Time since onset of weakness (less than 18 months vs. 18 months or longer),
- El Escorial and time since onset of weakness (El Escorial definite and less than 18 months vs. not both),
- Baseline symptom severity (all ALSFRS-R questions scored 2 or greater vs. any question scored 0 or 1),
- Early disease state (all ALSFRS-R questions scored 2 or greater, SVC 80%-predicted or greater, and time since symptom onset less than 24 months vs. not meeting all three criteria),
- Baseline serum urate concentration (less than 5.5 mg/dL vs. 5.5 mg/dL or greater),
- Baseline serum NfL concentration (by median split),
- Baseline delta-FRS score (less than 0.47 points/year, 0.47 to less than 1.11 points/year, 1.11 points/year or greater),
- Site of onset (any bulbar onset, no bulbar onset),
- Site (individual sites with at least 5 participants per treatment group and all participants from sites with fewer than 5 participants per treatment group pooled).

For each classification, unknown, not reported, and missing will be considered one group. All individuals not included in a specified subgroup will be combined into a mixed, "other" group. The "other" group will be included in analyses if its prevalence is greater than 5%; otherwise, the "other" group will be excluded.

In cases where a model for a given subgroup and endpoint fails to converge, the covariance terms for the regimen-specific random effects will be simplified from unstructured covariance of intercepts and slopes to separate, uncorrelated variance components for intercepts and slopes. If convergence still fails, regimen-specific intercepts and slopes will be modeled as fixed effects. If convergence still fails, the participant-specific random effects will be simplified from unstructured covariance of intercepts and slopes to separate, uncorrelated variance components for intercepts and slopes.

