This Regimen-specific Statistical Analysis Plan (R-SAP) for the CNM-Au8 regimen (RGC) specifies any modification from the default outcome measures, analysis samples, and planned analyses for the placebo-controlled period of the HEALEY ALS Platform Trial as specified in the Master SAP (M-SAP). The M-SAP and this R-SAP supplement the Master Protocol, the "ALS Master Protocol Recommended Statistical Analysis, Design and Simulation Report" (Appendix 1 to the Master Protocol), and the RGC Regimen-specific Appendix (RGC RSA). Please refer to the Master Protocol and the RGC RSA for details on the rationale for the study design, eligibility criteria, conduct of the trial, clinical assessments and schedule of assessments, definitions and reporting of adverse events, data management conventions, and regulatory oversight and compliance procedures. The "ALS Master Protocol Recommended Statistical Analysis, Design and Simulation Report" (MPRDR) and any regimen-specific deviations described in the RGC RSA, and this R-SAP are authoritative in defining the primary and interim analyses. In case of discrepancies between the RGC RSA and this R-SAP concerning use of shared placebos, this R-SAP is authoritative. In case of discrepancies between either SAP and the Master Protocol and the RGC RSA concerning matters of analysis other than the primary and interim analyses and use of shared placebos, the M-SAP and this R-SAP are authoritative. In case of discrepancies between the M-SAP and this R-SAP, this R-SAP is authoritative. On all matters not related to analysis, the Master Protocol and the RGC RSA are authoritative. The following table describes relationships among the relevant documents in adjudicating possible discrepancies with higher numbers indicating greater authority.

Issues potentially requiring adjudication	Master Protocol	RGC RSA	MPRDR	M-SAP	RGC R-SAP
Use of shared placebos	1	4	2	3	5
Primary and interim analysis specifications not related to use of shared placebo	1	5	4	2	3
Statistical analysis specifications not related to use of shared placebo or primary and interim analyses	1	3	2	4	5
All matters not related to statistical analysis	4	5	1	2	3

2. Study Design

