5.1 ALSFRS-R

The definitions of ALSFRS-R scores are the same as described in the M-SAP. Pre-baseline slope in ALSFRS-R (delta-FRS) is defined as 48 minus the baseline ALSFRS-R total score then divided by the number of months from onset of symptomatic weakness to the Baseline Visit. The number of months will be calculated as the difference in days from onset of symptomatic weakness to the Baseline Visit multiplied by 12 / 365.25. The date of onset of symptomatic weakness will be imputed as the fifteenth day of a month if not specified more precisely.

ALSFRS-R domain scores are exploratory measures of the primary efficacy endpoint ALSFRS-R total score.

Time to first occurrence of a ≥ 6 -point decline in ALSFRS-R total score is a composite endpoint with death or death equivalent, whichever occurs first, and will be censored at the last date at which an ALSFRS-R assessment was performed up to the end of the Week 24 Visit window.

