where Y_{ij} is a given efficacy endpoint measured in participant i at visit j , $a_{k(i)}$ is a random intercept for regimen k to which participant i was assigned, v_j is an indicator variable for visit j , \mathbf{z}_i is the vector of covariates (centered time since onset, centered delta-FRS, centered baseline riluzole use, and centered baseline edaravone use) for participant i , t_i is an indicator variable for treatment t to which participant i was assigned, γ_1 , $\gamma_{2,j}$, $\boldsymbol{\gamma}_3$, $\gamma_{4,j}$, and $\boldsymbol{\gamma}_{5,j}$ are estimated parameters and vectors of parameters for the fixed effects, and ϵ_{ij} is the residual for participant i at visit j . The regimen-specific random effects are normally distributed with mean 0 and variance σ_r^2 . The vector of residuals for a given participant are normally distributed with mean $\mathbf{0}$ and an unstructured covariance matrix \mathbf{R} . The regimen-specific random effect for a given participant and residuals for that participant are uncorrelated.

The following SAS code specifies the model:

```
proc mixed data=xxx method=reml;
  class regimen id trtrnd visit;
  model Value = trtrnd|visit
            sx2b1|visit dFRS|visit rlz|visit edv|visit / solution cl;
  random intercept / subject=regimen type=vc;
  repeated visit / subject=id type=un;
```

where `id` is a participant study identifier, `trtrnd` is the randomly assigned treatment group, `visit` is the visit identifier, `Value` is value of the efficacy endpoint being tested for a given participant at a given visit, `sx2b1` is years since ALS symptom onset centered at the sample median, `dFRS` is pre-baseline slope centered at the sample median, `rlz` is an indicator of riluzole use at baseline, and `edv` is an indicator of edaravone use at baseline. The primary estimate will be the treatment-dependent difference in change from baseline to the Week 24 Visit. The estimate and its 95% Wald confidence bounds will be obtained by a linear contrast of adjusted means.

The estimand estimated by the primary linear contrast of the shared-baseline, repeated-measures linear mixed model is the mean difference in 24-week change from baseline of a given continuous efficacy endpoint in the two active treatment groups relative to the placebo group in the FAS population. The estimand is defined by the following attributes:

- Treatment: CNM-Au8 administered orally at dosages of 30 mg/d and 60 mg/d vs. placebo.

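### The delta-FRS subgroup cut-points are in points per year, but the SAP defines delta-FRS in points per month, a 12-fold unit mismatch

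*SAP*

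**What the plan says.** SAP Section 5.1 defines delta-FRS as "48 minus the baseline ALSFRS-R total score then divided by the number of months from onset of symptomatic weakness to the Baseline Visit". It then fixes the denominator as the "difference in days from onset of symptomatic weakness to the Baseline Visit multiplied by 12 / 365.25". The variable is therefore in points per month.

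SAP Section 6.5.12 uses the same named variable to form three groups: "Baseline delta-FRS score (less than 0.47 points/year, 0.47 to less than 1.11 points/year, 1.11 points/year or greater". The yearly unit is attached to all three categories. The section says these "additional subgroups will be analyzed in the random-slope model (see Section 6.5.5) for primary and secondary efficacy endpoints in the FAS analysis set".

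Where delta-FRS enters the models as a covariate, Section 6.5.3 says only that it "is pre-baseline slope centered at the sample median", with no unit and no rescaling. The protocol does not define delta-FRS.

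**The concern.** A cut-point and the variable it cuts must share a unit, and here they do not. Nothing says that delta-FRS is multiplied by 12 for this subgroup, and no second, annualised version is defined. Two programmers working from the same SAP could form different groups.

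Two things are at stake:

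- If the printed unit is applied, most participants land in the fastest group. The analysis then could not show whether the treatment effect varies with progression rate, and this is the only listed subgroup defined by pre-baseline progression rate. A nearly empty slowest group might also trigger the convergence fallbacks at the end of Section 6.5.12.
- If the monthly variable is compared directly with 0.47 and 1.11, the tables carry a label that is wrong by a factor of 12.

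A choice of unit made after unblinding would be a post hoc choice of subgroup boundaries.

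**Working it through.** **Inputs**

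- delta-FRS = (48 − baseline ALSFRS-R) / months, with months = days × 12 / 365.25 (SAP Section 5.1).
- Cut-points 0.47 and 1.11, labelled per year (SAP Section 6.5.12).
- Score limits "0 and 48 for ALSFRS-R total score" (SAP Section 6.5.10), so the least possible loss is 0; totals move in whole points.
- Reference times: 18 months, from the SAP's own split "Time since onset of weakness (less than 18 months vs. 18 months or longer"; 24 months, from the early-disease subgroup in the same section; 12 and 36 months for illustration.

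The plan gives no derivation of 0.47 or 1.11, so there is no calculation of its own to reproduce.

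**Step 1: the two readings on one scale**

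- Printed unit: 0.47 / 12 = 0.0392 and 1.11 / 12 = 0.0925 points per month.
- Section 5.1 unit: 0.47 × 12 = 5.64 and 1.11 × 12 = 13.32 points per year.

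**Step 2: points lost from 48 at each cut**

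Per-year reading: cut × months / 12. Per-month reading: cut × months.

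| Months since onset | Per-year cuts | Whole points for fastest group | Per-month cuts | Whole points for fastest group |
|---|---|---|---|---|
| 12 | 0.47, 1.11 | 2 | 5.64, 13.32 | 14 |
| 18 | 0.705, 1.665 | 2 | 8.46, 19.98 | 20 |
| 24 | 0.94, 2.22 | 3 | 11.28, 26.64 | 27 |
| 36 | 1.41, 3.33 | 4 | 16.92, 39.96 | 40 |

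**Step 3: time limits under the printed unit**

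- One point lost falls below the lower cut only after 1 × 12 / 0.47 = 25.5 months. Until then the slowest group requires a score of 48. That covers everyone under the 24-month limit of the early-disease subgroup.
- Two points lost stays in the fastest group until 2 × 12 / 1.11 = 21.6 months.
- Five points lost stays in the fastest group until 5 × 12 / 1.11 = 54.1 months.

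**Step 4: one participant, two groups**

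A score of 36 at 18 months gives 12 / 18 = 0.667 points per month, the middle group. Annualised, that is 0.667 × 12 = 8.0 points per year, the fastest group.

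**Step 5: how the groups might fill (assumptions, not trial data)**

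A grid of six scores (46, 44, 40, 36, 32, 28) by four times (12, 18, 24, 36 months) gives 24 profiles. The per-year reading puts 0 in the slowest group, 2 in the middle and 22 in the fastest. The per-month reading puts 13, 8 and 3.

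A simulation used baseline means of 34, 36, 38 and 40, SDs of 4, 5 and 6, and onset uniform over 3–36, 6–24, 12–60 or 3–60 months. That is 4 × 3 × 4 = 48 settings of 400,000 draws each, with score drawn independently of time since onset.

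| Reading | Slowest | Middle | Fastest |
|---|---|---|---|
| Per year, scores capped at 48 | 0.04–13.8% | not tabulated | 77.5–99.9% |
| Per year, scores above 48 excluded | 0.02–6.4% | not tabulated | 84.1–99.9% |
| Per month, scores capped at 48 | 7.0–86.5% | 13.2–57.4% | 0.3–38.1% |

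**Step 6: effect on the covariate**

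Multiplying a linear covariate by 12 divides its coefficient by 12 and leaves the treatment contrasts unchanged. The adjusted models are therefore unaffected.

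**The case against.** The strongest reply is that no one would implement the per-year reading. Section 5.1 gives an explicit formula, the SAP never tells anyone to multiply by 12, and the natural program compares that variable with 0.47 and 1.11 as they stand. On this view the harm is a mislabelled table row. A yearly threshold can also be converted to a monthly one, so the two sections are implausible together rather than logically incompatible. The classification is one of 17 listed in Section 6.5.12 and runs in a supportive model. The simulated percentages rest on baseline and onset distributions that the documents do not give, and the per-month ranges are too wide to say much.

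Much of this stands. The reach is small, monthly cuts are the likelier intent, and the simulation only illustrates. The SAP also accepts groups likely to be sparse elsewhere (weight of 150 kg or more, CKD stage 5), so uneven group sizes are not in themselves an error.

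It does not remove the problem. The yearly unit is printed three times in an operative rule. Section 6.5.3 already carries time since onset in years, so a programmer who divides points lost by years would be following Section 6.5.12 as written. The whole-point arithmetic in Steps 2 and 3 needs no assumed distribution. Even on the benign reading, the reported label is wrong by a factor of 12.

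The M-SAP and the SAP's reference list were not available, so a source for the cuts may exist there. The M-SAP could not override the R-SAP, because "In case of discrepancies between the M-SAP and this R-SAP, this R-SAP is authoritative" (SAP Section 1).

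**Conclusion.** The concern holds. Sections 5.1 and 6.5.12 of the SAP give the same variable in units that differ by a factor of 12, and nothing available reconciles them. As printed, two points lost before 21.6 months puts a participant in the fastest group, and the slowest group is closed to anyone below 48 until about 25.5 months. These figures follow from the SAP's own numbers. The estimate that 78% to 99.9% would fall in the fastest group depends on the assumptions in Step 5.

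The per-month reading is more plausible, but the documents do not confirm it. The consequence is confined to one subgroup classification, applied in the random-slopes model to the primary and secondary endpoints. The Bayesian primary analysis, the hierarchy in Section 6.5.1 and the covariate adjustment do not use these cut-points. It should be corrected, but it does not threaten the main conclusions.

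**What to change.** Before data lock, trace the source of 0.47 and 1.11 and restate the cut-points in Section 6.5.12 on the Section 5.1 scale.

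- If the source is per month, change the unit to points/month in all three categories.
- If per year was intended, say that delta-FRS is multiplied by 12 for this subgroup, and record that the slowest group is then expected to be nearly empty.

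The cost is one check of the source and a one-line SAP correction. No change to data collection or to any other analysis is needed.

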6.5.13 Comparison of Controls across Regimens

Comparisons of placebo participants across regimens are the same as specified in the M-SAP with separate analyses that include baseline serum NfL level as an additional covariate plus applicable interaction terms as relevant to a given model.

6.5.14 Pharmacokinetic Analyses of CNM-Au8

Pre-dose concentrations of CNM-Au8 in whole blood and plasma will be summarized by treatment group and visit in the ERO sample. Concentrations below the limit of quantitation (BLQ) will be replaced with one half of the lower limit of quantitation. Summaries will include number of observations, number and percentage with concentrations BLQ, arithmetic mean, median, standard deviation, minimum, maximum, geometric mean, geometric coefficient of variation (calculated as $\sqrt{\exp(\text{variance of log-transformed concentrations}) - 1}$), and 95% confidence bounds for the geometric mean assuming log-normally distributed data.

A concentration response relationship based on observed CNM-Au8 C_{\max} per active participant versus ALSFRS-R slope change will also be analyzed as an exploratory endpoint.

Whole blood and plasma concentration data of CNM-Au8 may be subjected to population pharmacokinetic analysis to derive population estimates of pharmacokinetic parameters and test the effect of various covariates such as age, weight, and sex. Details of the analysis will be described in a separate data analysis plan (DAP). This analysis may be performed by combining data from the current study with data from other studies of CNM-Au8, if deemed appropriate. The tests of association with ALSFRS-R and the population pharmacokinetic analysis will be performed by Clene Nanomedicine or its designee and reported in a separate modelling report.

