⁹ In addition to study visits outlined in the SOA, participants will be asked to complete twice weekly voice recordings at home.

¹⁰ Drug will only be dispensed at this visit if the participant continues in the OLE.

¹¹ Participants will only have a Follow-Up Safety Call at this time if they *do not* continue on in the OLE. Participants who continue into OLE will have a Follow-Up Safety Call after their last dose of study drug during the OLE phase.

¹² Whole blood and plasma will be collected prior to administration of the daily dose at the Baseline and Week 24 visit. Plasma will be collected prior to administration of the daily dose at the Week 4 and Week 8 visits. Refer to the RSA laboratory manual for collection and processing parameters.

¹³ Vital status, defined as a determination of date of death or death equivalent or date last known alive, will be determined for each randomized participant at the end of the placebo-controlled portion of their follow-up (generally the Week 24 visit, as indicated). If at that time the participant is alive, his or her vital status should be determined again at the time of the last patient last visit (LPLV) of the placebo-controlled portion of a given regimen. We may also ascertain vital status at later time points by using publicly available data sources as described in section 8.15 of the Master Protocol.

¹⁴ The maximum window between study visits during the placebo-controlled period may not exceed 64 days.

¹⁵ If the CSF collection is unable to be performed for logistical reasons, such as scheduling, at the Week 16 Visit, it may be performed at the Week 24 Visit.

¹⁶ Participants should be instructed to hold the study drug on the day of the study visit. Study drug should not be taken until after study visit procedures are complete.

¹⁷ Visit may be conducted via phone or telemedicine with remote services instead of in-person if this is needed to protect the safety of the participant due to a pandemic, or other reason.

¹⁸ If required due to pandemic-related restrictions, Forced Vital Capacity (FVC) performed by a Pulmonary Function Laboratory evaluator or with a study-approved home spirometer, or sustained phonation using a study approved method may be used for eligibility (Master Protocol Screening ONLY).

¹⁹ Two smartphone apps should be installed on the participant's phone, one to collect the voice recordings and one to collect home spirometry.

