8 BIOFLUID COLLECTION

8.1 Pharmacokinetic (PK) Assessments

8.1.1 Whole Blood PK Assessments of CNM-Au8

Samples for the measurement of whole blood concentrations of Au will be collected before (pre-dose) administration of investigational product per the Schedule of Assessments. PK collection and processing parameters are specified in the RSA laboratory manual.

PK analyses of CNM-Au8 will be specified in a separate PK analysis plan.

PK blood samples will be shipped to and analyzed under the responsibility of the Clene Nanomedicine, Inc.'s bioanalytical laboratory at:

Clene Nanomedicine, Inc.
Bioanalytics Laboratory
[name] [name] 21901-2912
USA

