⁸ At all visits, whether conducted in-clinic or via telemedicine (or via phone if telemedicine is not available), vital signs include systolic and diastolic blood pressure, heart rate, respiratory rate, and temperature. At all in-clinic visits, vital signs include weight. At the MP Screening Visit only, vital signs include height measured in cm.

⁹ If required due to pandemic-related restrictions, forced vital capacity (FVC) performed by a Pulmonary Function Laboratory evaluator or with a study-approved home spirometer or sustained phonation using a study-approved method may be used for eligibility (Master Protocol Screening ONLY).

¹⁰ Clinical safety labs include hematology (CBC with differential), complete chemistry panel, liver function tests, thyroid function, and urinalysis. Serum pregnancy testing will occur in women of child-bearing potential at the Master Protocol Screening Visit and as necessary during participation. Pregnancy testing is only repeated as applicable if there is a concern for pregnancy.

¹¹ Whole blood samples for CNM-Au8 PK, plasma samples for riluzole PK, and whole blood, plasma, and urine samples for PD biomarkers should be obtained prior to the first daily dose of study drug at each applicable clinic visit. The time of the most recent dose of study drug, the most recent meal prior to sampling, and the time of sample collection should be reported. Whole blood and urine will be collected only at the Baseline and Week 24/Early Termination visits.

¹² If the participant consents to DNA sample collection but a DNA sample is not obtained at the Baseline Visit or if that sample is not usable, a DNA sample can be collected after the Baseline Visit.

¹³ If the participant consents to CSF sample collection but a CSF sample is not obtained at the Week 16 Visit, a CSF sample can be collected at the Week 24 Visit.

¹⁴ Adverse events that occur after signing the RGC ICF will be recorded.

¹⁵ Two smartphone apps should be installed on the participant's phone, one to collect home spirometry and one to collect voice recordings.

¹⁶ In addition to study visits specified in the SoA for collection of voice recordings, participants should complete twice weekly voice recordings at home. During weeks when a participant completes a voice recording in-clinic, he or she should only complete one other voice recording at home.

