5.10 Pharmacokinetics of CNM-Au8

Whole blood and plasma samples collected at the Baseline and Week 24 visits will be analyzed to quantify the concentration of CNM-Au8. Details of the CNM-Au8 assay technique and analysis plan will be specified in a separate PK analysis plan. This plan will be finalized prior to database lock.

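### The exploratory concentration-response analysis is planned on an observed Cmax, but every scheduled CNM-Au8 sample is pre-dose, so the exposure variable would be a trough under the wrong name

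*SAP*

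**What the plan says.** SAP 6.5.14 defines an exploratory analysis: "A concentration response relationship based on observed CNM-Au8" Cmax per active participant, related to ALSFRS-R slope change. The same section opens differently: "Pre-dose concentrations of CNM-Au8 in whole blood and plasma will be summarized by treatment group and visit".

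The sampling rules all place the sample before the dose:

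- Protocol 8.1.1, whole-blood gold: samples "will be collected before (pre-dose) administration of investigational product per the Schedule of Assessments".
- Protocol placebo-controlled Schedule of Activities, footnote 12: "Whole blood and plasma will be collected prior to administration of the daily dose at the Baseline and Week 24 visit". The same footnote makes the Week 4 and Week 8 plasma samples pre-dose as well.
- SAP 2.9, footnote 11: samples "should be obtained prior to the first daily dose of study drug at each applicable clinic visit". It adds: "Whole blood and urine will be collected only at the Baseline and Week 24/Early Termination visits".
- SAP 2.9, footnotes 3 and 17: the morning dose is held on Week 4, 8 and 24 visit days, and the first dose follows the Baseline procedures.

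SAP 5.10 says which samples are assayed for the drug: "Whole blood and plasma samples collected at the Baseline and Week 24 visits will be analyzed to quantify the concentration of CNM-Au8". It leaves the assay and analysis details to a separate PK plan. SAP 6.5.14 adds that population PK modelling may be done under its own plan, but does not link that model to the Cmax in this analysis.

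**The concern.** Cmax is the highest concentration reached after a dose, and observing it requires post-dose samples. If none are taken, an analyst following SAP 6.5.14 literally has no variable to enter. The likely outcome is that a pre-dose value is used and reported as Cmax, and a reader would take the result as a relationship with peak exposure when it is one with trough exposure.

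A second issue follows. Once the variable is understood to be a trough, its meaning depends on when the last dose was taken, and the SAP has no rule for samples drawn from people who have stopped drug. If early termination is related to progression, low concentrations in those participants would accompany fast decline without any drug effect.

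**Working it through.** No sample size, power or alpha is attached to this analysis, so there is no figure of the plan's own to reproduce. The check is a count of samples, followed by an illustration of how far a trough could lie from a peak.

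**1. Scheduled samples in the placebo-controlled period**

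| Visit | Timing | Whole blood | Plasma | Stated use of plasma |
|---|---|---|---|---|
| Baseline | before any drug | yes | yes | CNM-Au8 (SAP 5.10); riluzole (SAP 5.14); PD (SAP 5.13) |
| Week 4 | pre-dose | no | yes | PK, drug not named (protocol 6.4); riluzole (SAP 5.14); PD (SAP 5.13) |
| Week 8 | pre-dose | no | yes | as Week 4 |
| Week 24 / Early Termination | pre-dose | yes | yes | CNM-Au8 (SAP 5.10); PD (SAP 5.13); PD only (protocol 6.8) |

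Post-dose samples: 0 + 0 + 0 + 0 = 0.

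The open-label extension adds none. Protocol 6.11.5 and 6.11.8 hold the dose until visit procedures are complete, and SAP section 1 limits the SAP to the placebo-controlled period.

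**2. On-treatment CNM-Au8 values per participant**

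- Under SAP 5.10: 2 visits assayed, less 1 drug-free Baseline, leaves 1 (Week 24).
- If Week 4 and Week 8 plasma is also assayed for gold: 1 + 2 = up to 3 plasma values.

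The documents disagree on which applies. The SAP 2.9 table marks CNM-Au8 PK samples at Weeks 4 and 8 when the visit is in clinic. The protocol schedule and protocol 6.4 also list PK blood at those visits. SAP 2.9 footnote 11 instead assigns whole blood to CNM-Au8 PK and plasma to riluzole PK, SAP 5.14 uses the Week 4 and 8 plasma for riluzole, and SAP 5.10 names only Baseline and Week 24 for CNM-Au8. On either reading, every value is a trough.

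**3. How far the trough could be from the peak**

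The documents give no half-life, so a range is assumed. For a one-compartment model at steady state with instant once-daily input,

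peak / trough = 2^(24 / half-life in hours).

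| Assumed half-life (h) | 12 | 24 | 48 | 72 | 168 | 504 |
|---|---|---|---|---|---|---|
| Peak / trough | 4.0 | 2.0 | 1.41 | 1.26 | 1.10 | 1.03 |

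Instant input makes these upper bounds within that model. Protocol 5.10.1.2, drawing on rodent and canine data, expects slow absorption and elimination with accumulation. That points to the right-hand end of the table but does not fix a value.

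**4. Samples taken off drug**

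Protocol 6.10 allows an Early Termination Visit after the safety call, which is about 28 days (672 h) after the last dose. It also lets participants stop drug and remain on study, so a Week 24 sample may be off drug. Relative to an ordinary 24 h trough, the fraction left at 672 h is 2^(−(672 − 24) / half-life):

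- half-life 168 h: 2^(−648/168) = 2^(−3.86) = 0.07;
- half-life 504 h: 2^(−648/504) = 2^(−1.29) = 0.41.

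So even where slow elimination makes peak and trough nearly equal, an off-drug sample can be a very different quantity.

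**The case against.** The strongest reply has four parts.

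- *Cmax here just means the highest measured concentration.* Nothing in the SAP defines it so. Under SAP 5.10 it would be a single value; with Week 4 and 8 plasma it would be the largest of up to three pre-dose values. The reply does show that the analysis can be run on some number, so what stands is that the label is wrong.
- *The separate PK plan or modelling report may define the metric.* Those documents were not available, and they may. They cannot create a post-dose sample, however, and SAP 6.5.14 already specifies an observed value. A peak predicted by a population model would be legitimate, but it would not be observed.
- *Elimination is slow, so trough approximates peak.* This may well be true and it limits the numerical harm. It is not a reason to keep the wrong name, and it does not help with samples taken after drug was stopped.
- *The analysis is one exploratory sentence.* This is correct. SAP 3.5 plans the dose comparisons separately, also as exploratory, and the primary analysis and testing hierarchy in SAP 6.3 and 6.5.1 do not use concentration data.

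**Conclusion.** The point holds, within limits. As written, SAP 6.5.14 names an exposure metric that no scheduled sample measures. This affects every active participant. What would be analysed is a trough: one Week 24 value under SAP 5.10, or the largest of up to three plasma values if the Week 4 and 8 plasma is assayed for gold. The finding rests on the documented sampling schedule alone; only the peak-trough and off-drug ratios depend on assumed half-lives.

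A reader might infer more than the documents support:

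- *That each person certainly has only one on-treatment value.* The documents conflict on Weeks 4 and 8.
- *That a relationship reported against this variable would be numerically wrong.* With slow elimination the gap may be a few percent, and a trough is a valid exposure measure if named as one.
- *That the trial's dose finding depends on this analysis.* Dose-group contrasts are planned separately.
- *That the mislabel is what prevents comparison with the Phase 1 exposures.* Those in protocol 5.6 are AUCs, so neither a Cmax nor a trough would be directly comparable.

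Primary and key secondary inference is unaffected.

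**What to change.** In SAP 6.5.14, replace observed Cmax with pre-dose (trough) concentration, and state:

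- which visit or visits and which matrix (whole blood or plasma) supply the value, and how several values are combined if more than one is used;
- that the dose and sample times already requested in SAP 2.9 footnote 11 will be used to flag Early Termination or Week 24 samples taken off drug, with a sensitivity analysis excluding them;
- that if the population PK model is built, AUC or Cmax from it may be used as exposure but will be labelled model-predicted.

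Reconcile the protocol schedule, protocol 6.4 and 6.8 and the SAP 2.9 table with SAP 2.9 footnote 11, 5.10 and 5.14 on whether Week 4, Week 8 and Week 24 plasma is assayed for CNM-Au8. Make the change before database lock, the deadline SAP 5.10 sets for the PK plan.

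The cost is small: SAP wording, with no new samples. The separate PK plan must be brought into line, and choosing Week 24 alone would set aside any Week 4 and Week 8 plasma values that are assayed.
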